3.2 Variables

The primary variable of this study (and also effectiveness endpoint) is:

- the percentage of patients achieving SVR12 (single last HCV RNA <50 IU/mL 12 weeks [i.e. at least 84 days] after the last actual dose of the ABBVIE REGIMEN) is the primary effectiveness endpoint.

The secondary variables of this study are:

- effectiveness endpoints:
 - the percentage of patients with virological response (HCV RNA <50 IU/mL) at EoT;
 - the percentage of patients with relapse after EoT (defined as HCV RNA >50 IU/mL at EoT followed by HCV RNA ≥ 50 IU/mL);
 - the percentage of patients with relapse during treatment phase¹ (defined as at least one documented HCV RNA <50 IU/mL followed by HCV RNA ≥ 50 IU/mL during treatment);
 - the number and percentage of patients meeting each and any of the following SVR12 non-response categories:
 - relapse during post-treatment phase (defined as HCV RNA <50 IU/mL at EoT or at the last on-treatment HCV RNA measurement followed by HCV RNA ≥ 50 IU/mL post-treatment);
 - missing SVR12 data and/or none of the above criteria;
 - descriptive statistics for baseline characteristics;
 - the number and percentage of patients with comorbidities and concomitant medications;
 - the number and percentage of patients with adverse events.

4 Study design

4.1 General study design and plan²

This is a post-marketing, prospective, multicenter, observational study in patients receiving the interferon-free ABBVIE REGIMEN (Paritaprevir/r – Ombitasvir \pm Dasabuvir) without RBV.

This study is focusing on collecting real-world data. Adult patients chronically infected with HCV and compensated liver cirrhosis, receiving the interferon-free ABBVIE REGIMEN will be offered to participate in this study during a routine clinical visit at the participating sites. The prescription of a treatment regimen is at the discretion of the physician in accordance with local clinical practice and label, is made independently from this observational study and precedes the decision to offer a patient the opportunity to participate in this study.

After written Authorization (Consent) for Use/Disclosure of Data form (hereinafter – written patient authorization form) has been obtained, patient data including demographic data, HCV disease characteristics, co-morbidities, co-medication, treatment details, and laboratory assessments as recorded in the patient's medical records (source documentation) will be documented in the eCRF. Information for patients enrolled within 2 weeks after initiation of ABBVIE REGIMEN is collected at routine patient visits therefore baseline patient data should be taken from medical records. No patient identifiable information will be captured, a unique

¹ The EoT time point is included in the analyzed interval.

² This section is based on the sections 9.1 "Study Design" and 9.8 "Description of Activities" of clinical study Protocol.

P16-253 (CITRIN) _ STATISTICAL ANALYSIS PLAN _ FINAL 2.0 _ 16 Mar 2018

patient number will be automatically allocated by the web based eCRF system once the investigator or designee creates a new patient file.

Follow-up visits, treatment, procedures and diagnostic methods will follow physicians' routine clinical practice.

In the study, patients will be observed for the duration of the ABBVIE REGIMEN therapy and for up to 12 weeks after treatment completion. 12-week routine treatment regimen will include at least two observational visits (Visit 1 and EoT) plus one 30 days safety follow-up visit and one 12 weeks follow-up visit (SVR12) after the last dose of ABBVIE REGIMEN. 30 days safety follow-up visit can be done as telephone call contact. Additional observational visits between Visit 1 and EoT can be done in case of clinical necessity and physician decision.

In total, there will be at least four study visits. Patients who prematurely discontinue the study should return to the site to document EoT data.

The schedule of the study procedures is presented in table 4.1.

Table 4.1 – Program activities

| Assessment/ Procedure (only available data to be collected; no diagnostic or monitoring procedures to be applied to the patients apart from those of routine clinical practice) | Visit 1 | Treatment period | | Post-treatment period | |
|--|---------|------------------------------|------------------------|-----------------------|-----------------|
| | | EoT (on-treatment visits) | Safety Follow-up visit | SVR12 | Follow-up visit |
| Written patient authorization form | X | | | | |
| Inclusion/Exclusion Criteria | X | | | | |
| Demographic information | X | | | | |
| IL28B | X | | | | |
| Relevant CHC disease characteristics | X | | | | |
| Liver fibrosis stage | X | | | | |
| CHC treatment history | X | | | | |
| HCV genotype and subtype | X | | | | |
| HCV RNA samples | X | X | | | X |
| Clinical chemistry and hematology | X | X | | | X |
| ABBVIE REGIMEN initiation documentation | X | | | | |
| ABBVIE REGIMEN adherence | X | | X | | |
| Concomitant medication | X | X | | | X |
| Relevant medical history, co-morbidities | X | | | | |
| SAE, non-serious AE and pregnancy reporting | X | X | X | X | X |

Time windows for reported clinical laboratory test results are described in the table 4.2.

Table 4.2 – Analysis time windows

| Time point | Time Window |
|------------------|--|
| Visit 1 | Last value prior to start of study treatment (i.e. \leq study day 1) |
| EoT ¹ | Study day of last dose (from study day 56 to study day 98) |
| SVR12 | last value between 57 and 112 days post the study day of last dose |

¹ The EoT time window will not be used for the target population analyses, actual collected EoT visit will be presented in this case even if $EoT \leq$ study day 55 (less than 8 weeks).

P16-253 (CITRIN) _ STATISTICAL ANALYSIS PLAN _ FINAL 2.0 _ 16 Mar 2018

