9.13 Data Analysis

9.13.1 Analysis Population, Time Windows and Handling of Missing Data

The target population (TP) is defined as all patients who fulfill the inclusion/exclusion criteria. The core population (CP) is defined as all patients of the TP, who have started the treatment combination recommended in the current local label for their disease characteristics. Patients not receiving the treatment recommended in the local label will be summarized in the non-core population (NCP). In addition, the core population with sufficient follow-up data (CPSFU) is defined as all CP patients, who fulfil one of the following criteria:

- (1) evaluable HCV RNA data ≥ 84 days after the last actual dose of the ABBVIE REGIMEN (i.e. data within the SVR12 time window)

- | (2) a HCV RNA value ≥ 50 IU/mL at the last measurement post-baseline (i.e. no virological response achieved at the last measurement on-treatment or post-treatment)
- | (3) HCV RNA < 50 IU/mL at the last measurement post-baseline, but no HCV RNA measurement ≥ 84 days after the last actual dose of the ABBVIE REGIMEN due to reasons related to safety (e.g. dropped out due to AE) or incomplete efficacy information (e.g. virologic failure such as relapse is reported in the eCRF but date and value of the corresponding HCV RNA test is missing). This means only patients who had virological response at their last on-treatment or post-treatment measurement, but had no HCV RNA measurements ≥ 84 days post-treatment for reasons not related to safety or effectiveness (e.g. lost-to-follow-up or patient not willing to perform an additional HCV RNA test ≥ 84 days post-treatment) will be excluded from this analysis.

The Safety Population (SP) is defined as all patients who received at least one dose of the ABBVIE REGIMEN.

In accordance with the non-interventional nature of the study all HCV RNA measurements will be performed at the sole discretion of the physician and all HCV RNA measurements have to be entered into the eCRF. All recorded HCV RNA values will be assigned to appropriate time points (Visit 1, additional on-treatment visits (if any), EoT visit, 30 days safety follow-up visit and SVR 12 follow-up visit). The time windows for the assignments will be specified in the statistical analysis plan (SAP).

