9.13.7 Clinical Laboratory Data

All reported clinical laboratory test results will be assigned to one of the time points using the time windows specified in the table below.

Table 1 - Analysis Time Windows

Time point	Time Window
Visit 1	Last value prior to start of study treatment (i.e. ≤study day 1)
Actual EoT	Study day of last dose (28 days prior to EoT - 14 days post EoT)
12 weeks (day 85 post EoT)	57 – 112 post EoT

Mean changes from baseline to each post-baseline visit will be summarized descriptively.

Laboratory data values collected during the treatment period will be categorized as low, normal, or high based on reference ranges used in this study. The number and percent of patients who experience post-baseline shifts during treatment in clinical laboratory values from low/normal to high and high/normal to low based on the reference range will be summarized.

Additional details of the analyses of clinical laboratory data will be specified in the SAP.

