4.3 Planned analyses

The only final statistical analysis report will be performed for this study.

No analyses for DMC meetings and no interim analysis are planned in the study.

5 General considerations

Study Day will be calculated from the reference start date, and will be used to show start/stop day of assessments and events.

Reference start date is defined as the day of the start treatment (“EXSTDTC” variable from “EX” domain of the database).

If the date of the event is on or after the reference date then

study day = (date of event – reference date) + 1.

If the date of the event is prior to the reference date then

study day = (date of event – reference date) – 1.

Baseline is defined as the measurement taken on Visit 1.

6 Analysis populations

The target population (TP) – all patients with signed written Patient Authorization, who fulfill the eligibility criteria. Patients who prematurely discontinue earlier than ≤study day 55 will be used in analyses on the target population with actual EoT time point without windowing conventions adjustment for EoT.

The core population (CP) – all patients of the TP, who have started and received the treatment combination recommended in the current local label for their disease characteristics. Patients with EoT ≤ study day 55 (less than 8 weeks) will be excluded from the CP (these patients will be included to the NCP).

The safety population (SP) – all patients who received at least one dose of the ABBVIE REGIMEN.

The non-core population (NCP) – patients not receiving the treatment recommended in the local label.

The core population with sufficient follow-up data (CPSFU) – all CP patients, who fulfill one of the following criteria:

- evaluable HCV RNA data within the SVR12 time window;

¹ This section is based on the section 9.1.1 “Study Size” of clinical study Protocol.

P16-253 (CITRIN) _ STATISTICAL ANALYSIS PLAN _ FINAL 2.0 _ 16 Mar 2018

- a HCV RNA value ≥ 50 IU/mL at the last measurement post-baseline (i.e. no virological response achieved at the last measurement on-treatment or post-treatment);
- HCV RNA <50 IU/mL at the last measurement post-baseline, but no HCV RNA measurement on the SVR12 visit due to reasons related to safety (e.g. dropped out due to AE) or incomplete efficacy information (e.g. virologic failure such as relapse is reported in the eCRF but date and value of the corresponding HCV RNA test is missing).

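### SAP Table 4.2 replaces the protocol's end-of-treatment window, set around each patient's actual last dose, with fixed study days 56 to 98; the two agree only for a last dose on day 84

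*SAP*

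**What the plan says.** Protocol 9.13.7, Table 1, calls the time point actual EoT and sets its window as "Study day of last dose (28 days prior to EoT - 14 days post EoT". SAP 4.1, Table 4.2, has "Study day of last dose (from study day 56 to study day 98". The SVR12 row of the same SAP table remains tied to each patient's last dose: "last value between 57 and 112 days post the study day of last dose".

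Three further provisions set the scope:

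- Footnote 1 to Table 4.2 exempts one population: "The EoT time window will not be used for the target population analyses, actual collected EoT visit will be presented in this case".
- SAP section 6 repeats that exemption and sets a floor for the CP: "Patients with EoT ≤ study day 55 (less than 8 weeks) will be excluded from the CP". A patient with EoT from day 56 onward can therefore be in the CP.
- Protocol 9.13.1 says of HCV RNA values: "The time windows for the assignments will be specified in the statistical analysis plan (SAP". Table 4.2 is the only window table in the SAP, although its introductory sentence mentions laboratory results only.

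SAP section 15 states that nothing departs from the protocol.

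**The concern.** A window tied to last dose follows the patient, and a window in fixed study days does not. The SAP expects treatment durations other than 84 days: section 9 has a category for premature discontinuation, and the Table 3.1 shell lists reasons for deviating duration. For such patients the fixed window can take in samples drawn well after treatment stopped, or miss samples drawn at its end.

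EoT virological response is a secondary endpoint and one of the starting points for relapse after treatment. The EoT row has no rule for choosing among several values in the window, whereas the SVR12 row takes the last. A footnote to SAP 3.2 also counts the EoT time point within the interval for relapse during treatment. A positive sample taken after treatment but labelled EoT could therefore be reported as EoT non-response or as breakthrough. In the laboratory tables, change from baseline to EoT would mix values on and off drug.

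**Working it through.** **Inputs.** The protocol window is last dose −28 to +14 days (Protocol Table 1). The SAP window is days 56 to 98, and its SVR12 window is last dose +57 to +112 (SAP Table 4.2). Day 1 is the first dose, because SAP section 5 has "study day = (date of event – reference date) + 1" with treatment start as the reference. The planned duration is 12 weeks (SAP 4.1: "12-week routine treatment regimen will include at least two observational visits (Visit 1 and EoT").

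**Reproducing the SAP figure.** The planned last dose is on day 12 × 7 = 84. The protocol window is then 84 − 28 = 56 to 84 + 14 = 98, exactly the SAP's limits. The SAP has worked out the protocol window for one last-dose day and applied it to all.

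**Other last-dose days.** For last dose on day L:

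- Shared days = max(0, min(L + 14, 98) − max(L − 28, 56) + 1), out of 43.
- Longest time off drug still counted as EoT under the SAP = 98 − L (the protocol allows 14).

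| L | Protocol window | Shared days of 43 | Longest time off drug (SAP) | Last-dose-day sample in SAP window? |
|---|---|---|---|---|
| 56 | 28–70 | 15 | 42 | yes |
| 60 | 32–74 | 19 | 38 | yes |
| 70 | 42–84 | 29 | 28 | yes |
| 83 | 55–97 | 42 | 15 | yes |
| 84 | 56–98 | 43 | 14 | yes |
| 91 | 63–105 | 36 | 7 | yes |
| 98 | 70–112 | 29 | 0 | yes |
| 100 | 72–114 | 27 | none | no |
| 127 | 99–141 | 0 | none | no |

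For example, L = 60 gives 74 − 56 + 1 = 19, and L = 100 gives 98 − 72 + 1 = 27.

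**Early stoppers in the CP (L = 56 to 83).** Samples from 15 up to 98 − L days off drug are added. On-treatment samples before day 56 that the protocol would accept are dropped: days 28 to 55 at L = 56, and day 55 alone at L = 83.

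**Late finishers.** For L = 85 to 98 the last-dose-day sample is kept, but samples after day 98 are lost (day 99 at L = 85; days 99 to 112 at L = 98). From L = 99 the last-dose-day sample is outside the window.

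**Safety-population laboratory tables.** No exemption applies here. For L ≤ 55, every sample on days 56 to 98 is after last dose. The SVR12 window opens on day L + 57, which is no later than day 98 when L ≤ 41, so one sample can then fit both time points. At L = 20 the SVR12 window opens on day 77 and shares 98 − 77 + 1 = 22 days with EoT. The protocol's EoT window ends at L + 14 and cannot meet a window that opens at L + 57.

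**Scale.** If all 60 planned patients were in the denominator, one misassigned patient would move the EoT rate by 1/60 = 1.7 percentage points.

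**The case against.** The strongest reply is that the SAP cell can be read as limiting which last-dose days qualify, not which samples do. SAP section 6 and footnote 1 treat EoT as the patient's own study day with a cut at 55/56, which supports that reading. On it, the off-drug effect disappears. Patients finishing after day 98 would still fall outside EoT, and the protocol's parallel wording favours a sample window. A line open to two readings needs rewriting in any case.

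A second reply is that the table covers laboratory data only, as its introductory sentence says. Extension to HCV RNA is indeed an inference, but a strong one. The protocol hands HCV RNA windows to the SAP, this is the only window table, and the CPSFU definition applies an SVR12 window to HCV RNA. The target-population exemption would also have little purpose otherwise, because post-baseline laboratory tables are planned for the safety population.

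Three further limits stand:

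- A reader might infer that relapses are lost. Take a patient who stops on day 60 with a negative result and is positive on day 90. The day-60 negative is itself in the window, and the relapse definition in SAP section 9 also accepts the last value on treatment as its starting point. The patient can still meet it. The activity tables schedule no HCV RNA sample at the 30-day contact, although protocol 9.13.1 lists that contact as a separate HCV RNA time point.
- A reader might infer that late finishers in general lose their EoT value. Most keep one. From day 99 it is lost only if no other sample falls on days 56 to 98 and the protocol's backward imputation (9.13.1) does not restore it. The SAP neither repeats nor revokes that imputation.
- The protocol window itself allows 14 days off drug, so only samples beyond that are new.

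**Conclusion.** The discrepancy is real and undeclared. The two windows coincide only for a last dose on day 84. If days 56 to 98 bound the sample, CP and CPSFU patients with last doses on days 56 to 83 can have values 15 to 42 days off drug labelled EoT. Those finishing late can lose post-dose samples or, from day 99, the last-dose-day sample. The effect on HCV RNA rests on the inference that Table 4.2 governs it; the effect on the safety-population laboratory tables does not.

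What can go wrong is the EoT response rate, the sorting of non-responders between EoT non-response, breakthrough and relapse, and the EoT laboratory summaries. The documents do not support extending this to the primary endpoint: SVR12 remains tied to last dose, and target-population effectiveness analyses are exempt from the fixed window. The number of patients affected cannot be derived, because neither document gives a distribution of actual treatment duration. The point should be corrected, but it does not threaten the main result.

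**What to change.** In SAP Table 4.2, define the EoT window as running from 28 days before to 14 days after the date of the patient's last dose, as in protocol Table 1, for the CP, CPSFU and safety population. State that it applies to HCV RNA as well as laboratory values. Add a rule for several values in the window, for example the one closest to last dose; the protocol gives no such rule, so this is a choice to be stated in the SAP.

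Keep footnote 1 and the matching rule in SAP section 6. Removing them would take away the target population's use of the EoT visit as collected, and a value from a visit 20 days after last dose, now kept, would be lost.

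The cost is a short change of SAP wording and minor programming. The date of last dose is already needed for the SVR12 window, and the window does not change for patients who finish on day 84.

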9.0 Research Methods

9.1 Study Design

This is a prospective, multi-center observational study in patients receiving the interferon-free ABBVIE REGIMEN without RBV. The prescription of a treatment regimen is at the discretion of the physician in accordance with local clinical practice and label, is made independently from this observational study and precedes the decision to offer a patient the opportunity to participate in this study.

Adult patients chronically infected with HCV and compensated liver cirrhosis, receiving the interferon-free ABBVIE REGIMEN will be offered to participate in this study during a routine clinical visit at the participating sites.

After written Authorization (Consent) for Use/Disclosure of Data form has been obtained, patient data including demographic data, HCV disease characteristics, co-morbidities, co-medication, treatment details, and laboratory assessments as recorded in the patient's medical records (source documentation) will be documented in the electronic case report form (eCRF). Patients will be observed for the duration of the ABBVIE REGIMEN therapy and for up to 12 weeks after treatment completion. No patient identifiable information will be captured, a unique patient number will be automatically allocated by the web based eCRF system once the investigator or designee creates a new patient file.

This study is focusing on collecting real-world data. Follow-up visits, treatment, procedures and diagnostic methods will follow physicians' routine clinical practice.

12-week routine treatment regimen will include at least two observational visits (Visit 1 and EoT) plus one 30 days safety follow-up visit and one 12 weeks follow-up visit (SVR12) after the last dose of ABBVIE REGIMENT. Additional observational visits between Visit 1 and EoT can be done in case of clinical necessity and physician decision.

9.2**Product Supply**

As this is a post-marketing observational study, AbbVie is NOT involved in the product supply since the drug is being used according to the approved market label and is to be prescribed by the physician under usual, current medical practice and is clearly separated from the decision to include the patient in the study.

9.3**Setting**

For the purpose of this program participants will be recruited and observed in approximately 5-7 national and regional hospitals/outpatient services.

9.4**Program Duration**

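### The laboratory tables have no time point between Visit 1 and end of treatment, and the SAP's fixed end-of-treatment window also drops the on-treatment values of early stoppers

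*SAP*

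**What the plan says.** **Protocol 9.13.7.** All laboratory results are to be given a time point, and treatment-period values are to be classed as low, normal or high. The summary is to include "The number and percent of patients who experience post-baseline shifts during treatment in clinical laboratory values", in both directions. Table 1 in that section has three time points: Visit 1, actual EoT and 12 weeks after EoT. Its EoT window is "Study day of last dose (28 days prior to EoT - 14 days post EoT", so it moves with the patient's actual end of treatment.

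**SAP 4.1.** "Time windows for reported clinical laboratory test results are described in the table 4.2". The three rows of that table are:
- Visit 1: "Last value prior to start of study treatment", that is, up to study day 1.
- EoT: "Study day of last dose (from study day 56 to study day 98", the same fixed range for every patient.
- The row for the 12-week follow-up: "last value between 57 and 112 days post the study day of last dose".

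The footnote to the EoT row says "The EoT time window will not be used for the target population analyses". It does not mention the safety population.

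**SAP 10 and the table shells.** Safety, including laboratory data, is analysed on the safety population, which SAP section 6 defines as everyone with at least one dose. Shells 3.3.1 to 3.3.3 show Visit 1, EoT and SVR12 only, and the chemistry tables 3.4.1 to 3.4.3 are built the same way. SAP section 15 declares the SAP fully consistent with the protocol.

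**Visits before EoT.** Protocol 9.1 allows them: "Additional observational visits between Visit 1 and EoT can be done in case of clinical necessity and physician decision". Protocol 9.8 lists the laboratory tests to be documented at them.

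**The concern.** The protocol promises a count of patients with laboratory shifts during treatment, and collects laboratory values at on-treatment visits that could support it. The windows and shells have nowhere to put a value taken before the EoT window opens. A transient change in the first eight weeks that has resolved by EoT would appear in no summary, frequency or shift table.

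Patients who stop early are a separate problem. They belong to the safety population, and their on-treatment values matter for a tolerability objective. Under the protocol's moving window most of those values would count as EoT. Under the SAP's fixed window none would. With 60 patients planned, a few such patients can visibly change a shift table, and section 15 gives the reader no sign that anything differs from the protocol.

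**Working it through.** **Inputs.** Visit 1 runs to study day 1 and SVR12 runs from 57 to 112 days after last dose (both documents). The EoT window is 28 days before to 14 days after actual EoT (protocol Table 1), or study days 56 to 98 (SAP Table 4.2). SAP section 5 makes the first treatment day study day 1. Assumption: a 12-week course ends on day 12 × 7 = 84.

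**Reproducing the SAP window.** With last dose on day 84, the protocol rule gives 84 − 28 = 56 and 84 + 14 = 98. The SAP window is therefore the protocol window frozen at a nominal day-84 finish.

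**Completer, last dose day 84.** The unassigned on-treatment days are 2 to 55, which is 55 − 2 + 1 = 54 days. Day 1 counts as baseline, so the denominator is 84 − 1 = 83, and 54/83 = 65%. The result is the same under both tables.

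**Earlier last dose (day L).** The table gives post-baseline treatment days (2 to L) that fall in no window.

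| Last dose day | SAP Table 4.2 | Protocol Table 1 |
|---|---|---|
| 28 | 27 of 27 (100%) | 0 of 27 |
| 40 | 39 of 39 (100%) | 10 of 39 (26%) |
| 55 | 54 of 54 (100%) | 25 of 54 (46%) |
| 70 | 54 of 69 (78%) | 40 of 69 (58%) |
| 84 | 54 of 83 (65%) | 54 of 83 (65%) |

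For example, with L = 55 the protocol window opens on day 55 − 28 = 27, which leaves days 2 to 26, or 25 days.

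**Two readings of the SAP's EoT row, for a last dose on or before day 55.**
- If days 56 to 98 limit the day of last dose, the patient has no EoT laboratory value at all.
- If they limit the sample day, any EoT value is a post-treatment sample. The EoT and SVR12 windows then overlap whenever L + 57 ≤ 98, that is, L ≤ 41. With L = 20, SVR12 runs from day 77 to day 132, so days 77 to 98 belong to both. A sample labelled EoT would be 56 − 20 = 36 to 98 − 20 = 78 days after last dose.

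**Shift categories.** The protocol specifies low, normal and high. Shell 3.3.3 uses normal, abnormal not clinically significant and abnormal clinically significant. SAP section 15 does not list this difference either.

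**The case against.** The strongest reply is that the SAP did not create the main gap. Protocol Table 1 has the same three time points, and for a completer it gives the same days 56 to 98. That stands: for completers the conflict is between the protocol's own text and its own table, and the SAP carried it over. Only the loss for early stoppers is new in the SAP.

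The second reply is that the information is not lost. SAP section 8 lists all raw data, and listings 4.4 and 4.5.1 cover haematology and chemistry. Protocol 11.1.1 counts an abnormal laboratory finding as a possible adverse event, and SAP 10.2 tabulates treatment-emergent events with no day-56 cut. Early stoppers also keep their baseline and any SVR12-window values. All of this stands, but a listing is not the promised count of patients with shifts, and not every out-of-range value is reported as an adverse event.

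Third, SAP 10.4 speaks of parameters evaluated at each study visit, and Table 4.1 has a column headed EoT with on-treatment visits in brackets. One could read these as including on-treatment values, but no window or shell row carries them.

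A reader might go further and infer that the omitted values are the ones most likely to be abnormal, since extra visits follow clinical necessity. The documents do not support that. Protocol 9.8 also has these visits scheduled under routine practice, so ordinary monitoring is among them. For the same reason, the plan does not establish that the regimen will look safer than the data show. It may, and no more can be said.

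**Conclusion.** The point holds in two parts. Neither window table can deliver the treatment-period shift count that protocol 9.13.7 promises. In addition, the SAP's fixed window leaves anyone whose last dose is on or before day 55 with no post-baseline on-treatment value in the safety-population laboratory tables.

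For a completer the uncovered span is 54 of 83 post-baseline treatment days (65%), assuming a last dose on day 84. A reader might take this as the share of laboratory data lost, but it counts calendar days. Visits before EoT are optional and only available data are collected, so the share of values affected is unknown. So is the number of early stoppers. In the 60-patient study cited in protocol section 7 every patient completed treatment, so that number could be small.

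The consequence is possible understatement of on-treatment abnormalities in the summary, frequency and shift tables, with listings and adverse event tables as partial safeguards. It should be corrected, but it does not touch the primary endpoint.

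**What to change.** 1. For the safety-population laboratory tables, define the EoT window relative to the actual last dose, as in protocol Table 1. This recovers most early-stopper values and removes the overlap with SVR12. It changes nothing for completers, so step 2 is also needed.
2. Add an any-on-treatment row to SAP Table 4.2 and to shells 3.3.x and 3.4.x, covering study day 2 through last dose + 14 days. Report the number and percent of patients with any shift from baseline by low, normal and high, using the worst value per patient: the highest for upward shifts and the lowest for downward shifts. Include the parameters that protocol 9.8 lists for on-treatment visits: ALT, AST, GGT, total bilirubin, creatinine with creatinine clearance, haemoglobin and platelets. Protocol 9.8 does not list albumin or prothrombin time/INR at those visits, so include them only where recorded.
3. Correct the statement in SAP section 15 and list the differences that remain.

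The cost is SAP wording and one block of rows per laboratory table, with no new data collection. SAP section 2 allows revision before database soft lock; after that, the change needs an explanation in the study report. The drawback is that patients with more visits have more chances of a worst value, which a footnote should state.
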